#### 8 STUDY AGENT

Preparation of the scAAV9.U7.ACCA gene vector will be done by the Nationwide Children's Hospital Investigational Drug Services (IDS) according to the Manual of Operating Procedures (MOP). The vector will be delivered undiluted to the gene transfer venue at Nationwide Children's Hospital in 50mL Becton Dickinson Luer-Lok polypropylene syringe(s). It will be delivered at room temperature (not frozen) and administered to the subject within 24 hours of preparation. Handling of scAAV9.U7.ACCA vector will follow compliance standards for Biosafety Level 1 vectors: (http://osp.od.nih.gov/sites/default/files/NIH\_Guidelines.html)

The infusion rate will not be slower than the slowest rate at which the infusion set up compatibility testing was performed. The infusion rate will not approach or exceed 2 mL/kg/min (a rapid bolus rate) for any pediatric subject. The infusion will be given over approximately 60 to 90 minutes, incorporating competing concerns including maximizing uptake in the musculature and limiting sedation time versus limiting risk for IV infiltration and infusing slowly enough to observe for evidence of infusion reaction before entire dose is given. Depending on vector lot concentration, and other factors, infusion rate is expected to be around 0.03-0.08 mL/kg/min.

The vector will be flushed from the infusion tubing using 20 mL Lactated Ringer's/Hartmann's solution at the end of the infusion. The vector request, shipment, storage, preparation and management will be documented by the IDS.

## 8.1 Description of the Study Drug

	Investigational Product	
Product Name	scAAV9.U7.ACCA	
Dosage Form	The vector titer is based off linear qPCR and is stored in 2.0mL	
	vials, filled with 1.0 mL per vial.	
	All vials are 2.0mL screwcap polypropylene vials	
Unit Dose	$N = 1-3, 3.0 \times 10^{13} \text{ vg/kg}$	
Route of Administration	Intravenous injection of scAAV9.U7.ACCA via peripheral limb	
	vein	
Physical Description	scAAV9.U7.ACCA is provided frozen in vials. Once thawed,	
	scAAV9.U7.ACCA is a clear liquid	
Manufacturer	Nationwide Children's Hospital	
	Clinical Manufacturing Facility	
	[name]	
	[name]	

#### 9 STUDY PROCEDURES AND SCHEDULE

Subjects will complete 12 onsite visits and up to 5 local blood draws until 2 years post-transfer.

## 9.1 Study Visits

### 9.1.1 Screening (day -45 to day -1)

Informed consent will be obtained prior to the collection of any data and any study related procedures. Baseline measures from subjects will be obtained prior to gene transfer and will occur over two visits (up to 3 weeks apart). Because a pre-existing antibody response would be exclusionary, ELISA and ELISpot testing will be performed at the first visit, allowing the results to be reviewed prior to the open muscle biopsy and its subsequent risks (including sedation). The weight obtained at screening will be used to calculate the viral vector dose.

The following assessments will occur at these visits:

- Informed Consent
- Assent, if applicable
- Medical history
- Concomitant Medications
- Physical Exam
- Vital Signs (temperature, respiratory rate, heart rate, blood pressure, height (see Section 10.5 for more details), and weight)
- MRI of the lower legs (see Section 10.2 for more details)
- ECHO
- ECG
- Functional tests (variable depending on age of enrollment)
  - Enrollment age:  $\leq$  36 months
    - Bayley-IV scores (Bayley Scales of Infant and Toddler Development)
  - o Enrollment age: > 36 months and < 5 years of age
    - North Star Ambulatory Assessment (NSAA)

- Time to climb four stairs
- Amount of time required to walk 100 meters (100MWT)
- Enrollment age:  $\geq$  5 years old until Non-Ambulant
  - North Star Ambulatory Assessment (NSAA) score
  - Time to climb four stairs
  - Amount of time required to walk 100 meters (100MWT)
  - Force generated in knee flexion and extension in maximum voluntary isometric contraction (MVICT).
- Pulmonary functional tests (PFTs), including forced vital capacity. (See Section 10.3 for more details.)
- Open Muscle Biopsy (For details, see Section 10.2)

The following blood lab work will occur at this visit. (Lab work may be drawn over several days during visit if deemed necessary by study team except as noted above for ELISA and ELISpot.)

- Complete blood cell count (CBC) and differential, platelets
- Aspartate aminotransferase (AST)/alanine transaminase (ALT)
- Gamma-glutamyl transpeptidase (GGT)\*
- A Comprehensive Metabolic Panel (CMP) that includes:
  - Albumin/Serum total protein
  - Serum total bilirubin
  - Electrolytes
  - o Calcium
  - o Creatinine/Blood Urea Nitrogen (BUN)
  - Serum glucose
  - Alkaline phosphatase
- Prothrombin time (PT)/activated partial thromboplastin time (PTT)/INR
- Amylase
- Creatine kinase (CK)
- Cystatin C
- Total IgG
- D-Dimer\*\*
- Direct Bilirubin
- SC5b-9\*\*
- C3, C4\*\*
- CH50\*\*
- Antibody testing for Hepatitis B, C and HIV
- ELISA for detection of total antibodies to AAV9
- ELISpots for T-cell responses to AAV9 and Dystrophin
- Blood for vector shedding studies

\* For subjects taking drugs that potentially induce GGT synthesis through the cytochrome P450 system, the clinically significant range will be estimated starting at two times the levels obtained from the baseline screening test and up.

\*\* These laboratory tests have been recommended by the DSMB to be obtained at screening. These will not necessarily be exclusionary but having a baseline value will be helpful for comparison if a subject were to have any platelet or renal abnormalities that may be immune mediated after gene transfer.

The following urine lab work will occur at this visit:

- Urinalysis
- Urine for biobanking
- Urine for vector shedding studies

The following additional samples will be collected for vector shedding studies:

- Saliva
- Feces

For children under 10 kg in weight, the blood draw schedule will be reviewed to limit blood draw volumes to  $\leq 3\%$  of total body volume over a 24 hour period and  $\leq 10\%$  of total body volume over a 30 day period. The study team may deem it necessary to move or remove non-safety-related blood draws to other days if the volume drawn in one 24-hour period will be too near to 3% of total body volume.

Repeat testing of laboratory abnormalities within the screening period: Given the biologic variability inherent in some laboratory testing results, we will retest subjects with minimal and not clinically significant abnormalities resulting in values outside the NCH lab's normal range as defined by Table 7, such as minimal abnormalities of hemoglobin or CBC values. Similarly, subjects with anti-AAV9 endpoint titers at (but not above) the cutoff level of 1:400 will be retested for confirmation of titer. Normal values on the second of these tests will be considered to be acceptable for enrollment.

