#### 6 STUDY DESIGN AND ENDPOINTS

## 6.1 Overall Study Design

The proposed phase I/IIa clinical trial is an open-label trial where subjects will take part in a single injection study of self-complementary AAV9 carrying the ACCA snRNA under the control of a U7 promoter (scAAV9.U7.ACCA) delivered one time through a peripheral vein of the DMD subjects.

The comparison of muscle tissue from baseline and 90 days post-gene transfer will be the basis of the secondary efficacy analysis. Upon completion of the 2-year study period, subjects will be monitored annually as per standard of care for up to 5 years.

There will be at least 6 weeks between dosing of the first and second subjects within the cohort. The allowance of 6 weeks between dosing of the first and second subjects in the cohort provides time for an DSMB review of the safety analysis from five time points (Days 1, 2, 7, 14 and 30) prior to dosing of the next subject.

Notably, we have not required a 30 day time point between subsequent subjects because we wish to accommodate the realistic possibility that siblings may both enroll in the study, and viral shedding might possibly expose the second of each sibling pair to the vector, generating antibodies that are exclusionary to the trial. We would consider the burden on families of living apart for six weeks to be excessive, and the prospect of making parents choose between one or another of their sons to enroll to be ethically untenable.

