#### Exclusion Criteria

- 1. Active viral infection based on clinical observations.
- 2. Symptoms or signs of cardiomyopathy, including:
  - a. Dyspnea on exertion, pedal edema, shortness of breath upon lying flat, or rales at the base of the lungs
  - b. Echocardiogram with ejection fraction below 40%
- 3. Serological evidence of HIV infection, or Hepatitis B or C infection
- 4. Diagnosis of (or ongoing treatment for) an autoimmune disease
- 5. Persistent leukopenia or leukocytosis (WBC  $\leq$  3.5 K/ $\mu$ L or  $\geq$  20.0 K/ $\mu$ L) or an absolute neutrophil count < 1.5K/ $\mu$ L
- 6. Concomitant illness or requirement for chronic drug treatment that in the opinion of the SI creates unnecessary risks for gene transfer
- 7. AAV9 binding antibody titers  $\geq 1:400$  as determined by ELISA immunoassay
- 8. Abnormal laboratory values in the clinically significant range in Table 7, based upon normal values in the Nationwide Children's Hospital Laboratory

Table 7: Normal and abnormal laboratory values at Nationwide Children's Hospital Laboratory

System	Assay	Normal Range	Abnormal (Clinically Significant)
Liver Function	GGT	8-80 U/L	>80 U/L
	Total Bilirubin	0.1-1 mg/dL	≥3 mg/dL
	Direct Bilirubin	<0.6 mg/dL	>2 mg/dL
Renal Function	Cystatin C	0.3-1.3 mg/dL	>1.8 mg/dL
Hematologic Hemoglobin		(g/dL) 2 – 6 yrs: 11.5-13.5 6 – 12 yrs: 11.5-15.5	For all ages: $\leq 8 \text{ or } \geq 18 \text{ g/dL}$
		13-18 years: 13-15	-

Hematologic	White Blood Cells	4 – 6 yrs: 5.5-15.5 6 – 10 yrs: 5-14.5 10 – 21 yrs: 4.5-13.5	For all ages: White blood cell count $\leq 3.5 \text{ or } \geq 20 \text{ x } 10^3$ cells/mL OR Absolute neutrophil count of $\leq 1.5 \text{ x } 10^3 \text{ cells/mL}$
-------------	----------------------	--	--

\* For Hemoglobin, subjects will be excluded if they have a value less than the lower limit of normal for age at screening regardless of age. Abnormal but not clinically significant hemoglobin levels may be repeated during the screening period, and the subject accepted for enrollment if the results are not less than the lower limit of normal.

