#### 9.1.2 Gene Transfer Visit

#### 9.1.2.1 Pre Infusion Visit (Day -1)

Subjects will arrive at the Nationwide Children's Hospital within 24 hours prior to gene transfer.

The following assessments will occur at this visit:

- Medical history
- Concomitant Medications
- Adverse Events
- Physical Exam
- Vital Signs (heart rate, respiratory rate, temperature, blood pressure, height (see Section 10.5 for more details) and weight)

The following blood lab work will occur at this visit:

- Complete blood cell count (CBC) and differential, platelets
- Aspartate aminotransferase (AST)/alanine transaminase (ALT)
- Gamma-glutamyl transpeptidase (GGT)\*
- A Comprehensive Metabolic Panel (CMP) that includes:
  - o Albumin/Serum total protein
  - o Serum total bilirubin
  - Electrolytes
  - o Calcium
  - o Creatinine/Blood Urea Nitrogen (BUN)
  - o Serum glucose
  - Alkaline phosphatase
- Prothrombin time (PT)/activated partial thromboplastin time (PTT)/INR
- Creatine kinase (CK)
- Direct Bilirubin
- ELISpots for T-cell responses to AAV9 and Dystrophin
- Whole blood for biobanking

In previous gene therapy studies at NCH, there has been an observed antigen specific T-cell response to the AAV vectors. This is an expected response between 2 - 4 weeks following gene transfer. One possible consequence to such antigen specific T-cell responses is clearance of the transduced cells and loss of transgene expression. All subjects (ages 4 years and older) will already be on prednisone, prednisolone, or deflazacort for 12 weeks at time of enrollment as part of the inclusion criteria. The standard clinical dose of prednisone or prednisolone is 0.75 mg/kg/day, and the standard clinical dose of deflazacort is 0.9 mg/kg/day. In order to dampen the host immune response to our AAV-based therapy, for each subject the glucocorticoid dose will be increased to prednisone or prednisolone 1.0 mg/kg/day, not to exceed 60 mg/day; subjects on deflazacort at enrollment will be placed on prednisone or prednisolone for the immediate perinijection period. For subjects younger than 4 years of age who may not be on a corticosteroid,

\* For subjects taking drugs that potentially induce GGT synthesis through the cytochrome P450 system, the clinically significant range will be estimated starting at two times the levels obtained from the baseline screening test and up.

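### No AAV9 antibody test is scheduled between the first screening visit and Day 30, so a boy who seroconverts after screening can be infused undetected although he meets exclusion 7

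*Combined protocol and SAP*

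**What the plan says.** Section 7.1, exclusion 7, concerns "AAV9 binding antibody titers" of 1:400 or more by ELISA. It attaches no date relative to infusion.

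Section 9.1.1 sets a screening window of Day -45 to Day -1, with two visits up to 3 weeks apart, and fixes the ELISA to the earlier visit: "Because a pre-existing antibody response would be exclusionary, ELISA and ELISpot testing will be performed at the first visit". The reason given is that results can be reviewed before the open biopsy and its sedation. The section provides one ELISA retest: "subjects with anti-AAV9 endpoint titers at (but not above) the cutoff level of 1:400 will be retested for confirmation of titer".

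Section 9.1.2.1 (Day -1) lists "ELISpots for T-cell responses to AAV9 and Dystrophin" but no AAV9 ELISA. Section 9.1.3.3 adds the ELISA at Day 30. The ELISA row of Table 8 agrees: Screening, then Day 30.

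Section 6.1 treats the enrolment of brothers as realistic and warns that "viral shedding might possibly expose the second of each sibling pair to the vector, generating antibodies that are exclusionary to the trial". For that reason it sets no 30-day gap between later subjects. For the first pair it says "There will be at least 6 weeks between dosing of the first and second subjects within the cohort", to allow a DSMB review of five time points. It makes no exception if those two are brothers.

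**The concern.** An eligibility threshold on antibody status protects a subject only if it holds when the vector is given. Here the scheduled test can be more than six weeks old by then, and a boy who passed it has no scheduled recheck. The protocol itself describes how a boy's status might change in that interval, and it regards keeping brothers apart for six weeks as too great a burden, so contact at home is to be expected.

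Two things are at stake. The first is safety: a one-time systemic infusion that cannot be withdrawn could go to a boy whom the plan's own criterion would exclude. The second is interpretation. No scheduled test establishes antibody status at dosing. If the Day 30 ELISA is positive, antibody present before infusion cannot be told from antibody raised by the vector. Low vector genome counts or low dystrophin expression in that boy could then be put down to the product.

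**Working it through.** The plan gives no figure on this point to reproduce. The check traces the assay through the schedule and then does the timeline arithmetic.

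**Scheduled AAV9 ELISAs around infusion**

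| Time | Source | AAV9 ELISA |
|---|---|---|
| First screening visit, Day -45 at the earliest | 9.1.1, Table 8 | Yes |
| Later in screening | 9.1.1 | Only if the first titre is exactly 1:400 |
| Day -1 | 9.1.2.1, Table 8 | No (ELISpot only) |
| Days 0 to 14 | 9.1.2.2 to 9.1.3.3, Table 8 | No |
| Day 30 | 9.1.3.3, Table 8 | Yes |

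For a boy who screens below 1:400, the gap between scheduled ELISAs can reach 45 + 30 = 75 days, with the infusion inside it.

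**Inputs**

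- d = days from the second brother's ELISA to his own infusion, at most 45 (Section 9.1.1).
- g = days between the two brothers' infusions. If they are subjects 1 and 2, g is at least 6 × 7 = 42 (Section 6.1). For later subjects no minimum is set.

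**Formulas**

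- The ELISA predates the first brother's infusion by d − g days when d > g.
- Possible exposure time not covered by any required titre = the smaller of d and g.

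**Brothers as subjects 1 and 2**

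- Limiting case, g = 42 and d = 45: the sample is drawn 45 − 42 = 3 days before the first infusion, and the untested exposure is 42 days, all of it.
- With g of 45 or more, d − g cannot exceed 0, so a valid sample cannot predate the first infusion. The 3-day case therefore needs a gap of 42 to under 45 days and a draw at the start of the window.
- Later draws leave d days untested. If the two screening visits are the full 21 days apart and the second falls on Day -1, the first is on Day -22, so d is still at least 22.

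**Brothers as subjects 2 and 3**

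- Untested exposure is again the smaller of d and g. It is 0 if they are dosed on the same day and at most 45 days otherwise. Here the absence of a minimum gap does reduce the risk, as Section 6.1 intends.

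**Share of the data**

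- A sibling case needs at least two dosed subjects. One such boy is 1/2 = 50% of the data with two subjects and 1/3 = 33% with three.

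**Probability**

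- Not computable. The documents give no rate of transmission by shedding and no rate of seroconversion.

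**The case against.** The early ELISA has a sound purpose: it spares a boy who would be excluded an open biopsy under anaesthesia. That stands, and it is a reason to keep the early test. It does not argue against a second one.

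Section 9.1.2.1 starts the corticosteroid only once all eligibility criteria are passed, and it allows for a measure being repeated on Day -1. A repeat ELISA is therefore possible and would count. It is not required, however, and the ELISA is not named. A reader might infer that a seroconverted boy will be infused; the documents support only that he can be, without detection.

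Repeating the ELISpot on Day -1 is not odd in itself, since that series guides later steroid adjustment under Section 10.6.1. Other exclusionary tests, such as hepatitis and HIV serology and Cystatin C, are not repeated on Day -1 either. Both remarks are fair. What sets the AAV9 titre apart is that Section 6.1 describes how it might change during the trial.

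The 3-day figure is a corner case. A reader might infer that the whole shedding exposure is usually missed; it is missed entirely only when the sample predates the first infusion. A reader might also infer that brothers are likely to be subjects 1 and 2. The documents neither say so nor rule it out, and counting enrolment slots gives no probability. Nor can one boy be all of the data in the sibling case, because his brother has been dosed too.

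On interpretation, qPCR measures vector genomes in muscle directly, so poor delivery can be separated from poor skipping. It does not identify antibody as the cause. Whole blood is banked on Day -1, but no antibody assay on it is specified, and a later assay could not inform eligibility.

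**Conclusion.** The point holds. For a boy who screens below 1:400, no AAV9 ELISA is scheduled from the first screening visit, as early as Day -45, until Day 30 after infusion. Exclusion 7 can thus be met at dosing without anyone knowing, and the route that Section 6.1 foresees is not covered by a scheduled test. For brothers as subjects 1 and 2, the untested exposure is up to 42 days in the limiting case and otherwise the time from draw to infusion, up to 45 days.

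This assumes that the schedule is followed as written, that no unscheduled repeat is done, and that shedding can raise antibodies as Section 6.1 says it might. A screening titre below 1:400 means eligible; it does not mean antibody-free. The missing test is certain from the text. How often it would matter is unknown, and no claim is made about frequency. The change is cheap relative to what it protects and should be made.

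**What to change.** Keep the ELISA at the first screening visit. In Sections 9.1.1 and 9.1.2.1 and in Table 8, add a second AAV9 ELISA at a scheduled pre-dose draw. Time it as late as assay turnaround allows for the result to be reviewed before infusion, and after any household contact with a dosed subject. The documents do not give the turnaround, so the sponsor must set the day. State in Section 7.1 that exclusion 7 is judged on the most recent result before infusion, and use that value as the baseline for the Day 30 ELISA.

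Section 6.1 must also reconcile its 6-week interval between subjects 1 and 2 with its own sibling rationale. No new interval is proposed here; the present one serves DSMB review.

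The cost is one more run of an assay already in use and a short amendment. The extra blood is small but must fit the volume limits in Section 9.1.1 for boys under 10 kg. An occasional boy would be excluded after his baseline biopsy. The time between the second draw and infusion would remain untested, but it would be shorter.

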#### 9.1.2 Gene Transfer Visit

#### 9.1.2.1 Pre Infusion Visit (Day -1)

Subjects will arrive at the Nationwide Children's Hospital within 24 hours prior to gene transfer.

The following assessments will occur at this visit:

- Medical history
- Concomitant Medications
- Adverse Events
- Physical Exam
- Vital Signs (heart rate, respiratory rate, temperature, blood pressure, height (see Section 10.5 for more details) and weight)

The following blood lab work will occur at this visit:

- Complete blood cell count (CBC) and differential, platelets
- Aspartate aminotransferase (AST)/alanine transaminase (ALT)
- Gamma-glutamyl transpeptidase (GGT)\*
- A Comprehensive Metabolic Panel (CMP) that includes:
  - o Albumin/Serum total protein
  - o Serum total bilirubin
  - Electrolytes
  - o Calcium
  - o Creatinine/Blood Urea Nitrogen (BUN)
  - o Serum glucose
  - Alkaline phosphatase
- Prothrombin time (PT)/activated partial thromboplastin time (PTT)/INR
- Creatine kinase (CK)
- Direct Bilirubin
- ELISpots for T-cell responses to AAV9 and Dystrophin
- Whole blood for biobanking

In previous gene therapy studies at NCH, there has been an observed antigen specific T-cell response to the AAV vectors. This is an expected response between 2 - 4 weeks following gene transfer. One possible consequence to such antigen specific T-cell responses is clearance of the transduced cells and loss of transgene expression. All subjects (ages 4 years and older) will already be on prednisone, prednisolone, or deflazacort for 12 weeks at time of enrollment as part of the inclusion criteria. The standard clinical dose of prednisone or prednisolone is 0.75 mg/kg/day, and the standard clinical dose of deflazacort is 0.9 mg/kg/day. In order to dampen the host immune response to our AAV-based therapy, for each subject the glucocorticoid dose will be increased to prednisone or prednisolone 1.0 mg/kg/day, not to exceed 60 mg/day; subjects on deflazacort at enrollment will be placed on prednisone or prednisolone for the immediate perinijection period. For subjects younger than 4 years of age who may not be on a corticosteroid,

\* For subjects taking drugs that potentially induce GGT synthesis through the cytochrome P450 system, the clinically significant range will be estimated starting at two times the levels obtained from the baseline screening test and up.

prednisolone will be prescribed for the purposes of dampening the host immune response. This treatment will begin one day prior to the gene transfer and only after passing all inclusion and exclusion criteria (in the event that a measure is repeated on Day -1). All subjects will also be prescribed a proton pump inhibitor (PPI) for the purposes of dampening potential gastrointestinal upset related to the increased corticosteroid dosage. This corticosteroid and PPI regimen will be continued after gene transfer as discussed in Section 10.6.1, followed by a return to the pretreatment corticosteroid regimen.

